- Use of immunosuppressive or biological medication
- Pregnancy

METHODS

26 consecutive patients with pouchitis diagnosed by the symptoms and endoscopy. Patients are collected from the Helsinki University Central Hospital. Use of antibiotics or probiotics is not continued during the study. Fecal microbiota transplantation (FMT) is performed by experienced endoscopists using frozen and thawed stool through flexible sigmoidoscopy into the afferent limb. The second FMT is installed via catheter into the pouch 3 weeks after the first FMT. Antibiotic treatment has been stopped 36 hours before the FMT. 13 pouchitis patients receive a fecal transplantation from the healthy tested donor and 13 patients in the control group receive their own feces donated and prepared at the same day. The endoscopists and personnel performing the FMT are blinded for the type of feces. The randomization is done by a doctor not attending the study. Pouchscopy is assessed at 52 weeks to evaluate the endoscopic and mucosal healing. Clinical Pouchitis Disease Activity Index, see table 1 (Sandborn 1994) is assessed at week 4, 12, 26 and 52 and in addition to the endoscopy and histological index at weeks 0 and 52.

Table 1 Pouchitis Disease Activity Index (Sandborn 1994).

Table 1.
The Pouchitis Disease Activity Index⁴

Criteria	Score
Clinical	
Stool frequency	
Usual postoperative stool frequency	0
1–2 stools/day > postoperative usual	1
3 or more stools/day > postoperative usual	2
Rectal bleeding	
None or rare	0
Present daily	1
Fecal urgency or abdominal cramps	
None	0
Occasional	1
Usual	2
Fever (temperature > 37.8° C)	
Absent	0
Present	1
Endoscopic inflammation	
Edema	1
Granularity	1
Friability	1
Loss of vascular pattern	1
Mucous exudates	1
Ulceration	1
Acute histologic inflammation	
Polymorphic nuclear leukocyte infiltration	
Mild	1
Moderate + crypt abscess	2
Severe + crypt abscess	3
Ulceration per low-power field (mean)	
>25%	1
25–50%	2
>50%	3

Donors are excluded if they have taken antibiotics within the preceding 3 months; are on immunosuppressive or chemotherapeutic agents; have known or recent exposure to HIV; hepatitis B or C; have a current communicable disease; are morbidly obese; have IBD, IBS, atopy, chronic diarrhea or constipation; GI malignancy or polyposis; participate in high-risk sexual behaviors; use illicit drugs; have a history of recent incarceration or travel to areas with endemic diarrhea. Donor

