blood testing includes tests for HIV, hepatitis A, B and C; donor stool testing includes culture, *C. difficile* toxin, ova and parasites, and *Helicobacter pylori*.

Follow up of the patients include a telephone call after 12 and 26 weeks after the FMT, and a clinical control visit 52 weeks after the transplantation. The clinical part of the Pouchitis Disease Activity Index score is assessed during each call and clinical visit.

A general quality of life measurement (15D-questionnaire, www.15d-instrument.net) is done at the day of stool transplantation and 6 months after the transplantation. Any adverse events are recorded. Changes in the use of medication is recorded.

Fecal stool samples for phylogenetic analysis are collected before FMT and on weeks 4, 12, 26, and 52. Fecal calprotectin indicating level of inflammation is measured before FMT and on weeks 4, 12, 26 and 52.

Endpoint of the study is the remission defined as Pouchitis Disease Activity Index <7 and no need for antibiotic treatment of pouchitis during the 52-week follow-up. Secondary objective for this study include an evaluation of the changes in gut microbiota within the 52 weeks.

STATISTICAL ANALYSIS

The sample size is calculated in according to the estimation that the difference in remaining in remission is 55% (80 vs 25%) over 52 weeks. The calculated sample size is 26 patients and therefore 13 patients are selected for both groups (donor vs own feces). This difference is considered to be clinically meaningful. Confidence interval was selected to be 95% ($\alpha=0.05$ and $\beta=0.1$).

DATE

Patient collection will be made from September 2017 until June 2018. The follow up of the patients will end one year after the last patient included the study. Data analysis and reporting of the results will be during the year 2019.

ETHICAL ASPECTS

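### No primary test is named, and 13 per group gives 90% power only approximately: about 79% (Fisher) or 81% (unconditional exact) with a two-sided test that holds 5%

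*Combined protocol and SAP*

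**What the plan says.** The STATISTICAL ANALYSIS section is one short paragraph. The planning assumption is that "the difference in remaining in remission is 55% (80 vs 25%) over 52 weeks". The resulting size is given as "The calculated sample size is 26 patients and therefore 13 patients are selected for both groups (donor vs own feces"), and the error rates as "Confidence interval was selected to be 95% ($\alpha=0.05$ and $\beta=0.1"). METHODS enrols the same number: "26 consecutive patients with pouchitis diagnosed by the symptoms and endoscopy".

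The outcome is defined at the end of METHODS: "Endpoint of the study is the remission defined as Pouchitis Disease Activity Index <7 and no need for antibiotic treatment of pouchitis" over the 52 weeks. The endoscopic and histological parts of the index are scored only twice; METHODS lists them "in addition to the endoscopy and histological index at weeks 0 and 52".

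The document does not name a test for the comparison of the groups, its sidedness, the sample-size formula or the method for the confidence interval.

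**The concern.** Power belongs to a test. With 13 patients per group, the standard tests of two proportions differ markedly in both power and type I error, so a beta of 0.1 cannot be interpreted until the test is named.

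Two things are at stake. First, a null result would be read against a 10% chance of missing a 55-point effect, when the chance may be about twice that. Second, with no test fixed in advance, a borderline table could be significant by one standard test and not by another, and the choice could be made after the data are seen.

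**Working it through.** **Inputs.** From STATISTICAL ANALYSIS: p1 = 0.80, p2 = 0.25, d = 0.55, alpha = 0.05, beta = 0.1, n = 13 per group. Two readings are inferred. *Two-sided*: alpha 0.05 is paired with a 95% confidence interval. *Binary*: remission is a yes/no status, and the full index is available after baseline only at week 52. All 26 patients are taken as evaluable.

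**1. Reproducing the 13.** The unpooled large-sample formula is

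n = (z₀.₉₇₅ + z₀.₉₀)² × [p1(1−p1) + p2(1−p2)] / d²

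= (1.960 + 1.282)² × (0.1600 + 0.1875) / 0.3025 = 10.507 × 0.3475 / 0.3025 = 12.07, so 13 per group and 26 in total. This matches the plan.

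The pooled formula, with p̄ = 0.525, is

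n = [z × √(2p̄(1−p̄)) + z₀.₉₀ × √(p1(1−p1) + p2(1−p2))]² / d²

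- Two-sided (z = 1.960): (1.384 + 0.755)² / 0.3025 = 15.13, so 16 per group.
- One-sided (z = 1.645): (1.162 + 0.755)² / 0.3025 = 12.15, so 13 per group, which also matches.

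**2. Exact power and type I error at 13 per group.** There are 14 × 14 = 196 possible tables. Power is the total probability of the tables a test rejects when the arms are Binomial(13, 0.80) and Binomial(13, 0.25). Type I error is the same sum with one common rate in both arms, maximised over a fine grid of that rate.

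| Two-sided 5% test | Power, 80% vs 25% | Type I error at 25% common rate | Maximum type I error |
|---|---|---|---|
| Fisher | 78.7% | 1.8% | 2.9% |
| Unconditional exact (z-pooled; Boschloo rejects the same tables) | 81.0% | 4.7% | 4.9% |
| Uncorrected chi-square | 89.1% | 4.96% | 7.6% (at 50%) |

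The chance of missing the planned effect is 100 − 78.7 = 21.3% for Fisher and 100 − 81.0 = 19.0% for the unconditional exact test.

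**3. Is the shortfall only the price of conservative tests?** No. A linear programme over all rejection rules that treat the arms alike and keep type I error at or below 5% at every common rate on the grid gives a maximum power of 83.5%. No such test reaches 90% at this size.

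**4. Does the choice of test matter for the result?** Take 8/13 against 3/13. The pooled rate is 11/26 = 0.423, the difference is 5/13 = 0.385, its standard error is √(0.423 × 0.577 × 2/13) = 0.194, and z = 1.985.

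- Chi-square: p = 0.047
- Unconditional exact: p = 0.061
- Fisher: p = 0.111

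Chi-square and the unconditional exact test disagree in 6 of the 196 tables. Under 80% vs 25%, the probability that one of these tables occurs is 8.0%.

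**The case against.** A reader might infer that the sample size was miscalculated, or that 90% is simply wrong. The documents do not support either. The figure of 26 follows from the plan's own inputs by a standard formula. The plan never commits to Fisher or an unconditional exact test, so it cannot be in error for their power. An uncorrected chi-square comes within a point of 90%. This stands, and it is why the point is conditional on the test.

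Holding 5% at every common rate is also a standard that the plan does not state. If both arms sit at the planned control rate of 25%, chi-square has a type I error of 4.96%; the 7.6% needs a common rate twice as high. This narrows the criticism but does not remove it, because the error already passes 5% just above the planned rate (5.1% at 26%, 5.65% at 30%).

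Both readings are inferred. A one-sided 5% test would have exact power of 89.2% (unconditional exact) or 81.0% (Fisher), but it does not match a 95% interval. The phrase about remaining in remission, with clinical scores at weeks 4, 12, 26 and 52, leaves room for a time-to-relapse analysis; a log-rank simulation with assumed exponential times gave 85.3%. Neither alternative reaches 90%.

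Finally, 8/13 against 3/13 is a chosen example, with probability 1.7% under the planned rates. The 8.0% is the fairer measure of how often chi-square and the unconditional exact test would part.

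**Conclusion.** The point holds in conditional form. The arithmetic behind 26 is not wrong, but the 90% rests on a large-sample approximation or on a chi-square test whose type I error can exceed 5% at this size. With a two-sided test that holds 5%, power for 80% vs 25% is about 79% (Fisher) or 81% (unconditional exact), so the risk of missing the planned effect is about twice the stated 10%.

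This assumes a two-sided comparison, a binary endpoint and 26 evaluable patients. The documents give no expected loss to follow-up, so no figure for the effect of missing patients is offered. They give no interval method either, so the plan should not be charged with using an unsuitable one. Should be fixed; confidence in the figures is high.

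**What to change.** Keep 26 patients. Before unblinding, add a few sentences to STATISTICAL ANALYSIS that:

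- name one two-sided primary test that holds 5% at this size, unconditional exact or Fisher, at the sponsor's choice;
- restate power for that test with all 26 patients evaluable: about 81% (unconditional exact) or 79% (Fisher) for 80% vs 25%;
- report a 95% confidence interval that matches the test. For the unconditional exact test, this is the interval for the risk difference obtained by inverting the same test. For Fisher, it is the conditional exact interval for the odds ratio, with the observed risk difference beside it.

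The change is wording only; endpoint, enrolment and conduct stay as they are. The cost is a less favourable stated power. For comparison, at least 90% exact power for 80% vs 25% would take 34 patients with the unconditional exact test (90.8%) or 36 with Fisher (90.9%), before any allowance for dropout.
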